3.2.3.2. Daratumumab RP2D Rationale

The RP2D has been selected based on marked M-protein reduction with an acceptable safety profile in doses up to 16 mg/kg, the highest dose of Phase 1. MTD was not reached in Phase 1. The IDMC reviewed the safety data of 2, 4, 8 and 16 mg/kg cohorts and concluded that an acceptable benefit/risk profile was observed in doses up to 16 mg/kg. The majority of the Grade 3 adverse events were neutropenia, which was attributed to lenalidomide. The daratumumab/Len/Dex combination PK-profile was similar to daratumumab alone suggesting Len/Dex does not affect the pharmacokinetic profile of daratumumab.

The rationale of PR2D is also supported by the ongoing single agent daratumumab studies. Clinical pharmacokinetic data have shown the 16 mg/kg dose to be the lowest dose that results in complete target suppression at all time points. This dose and schedule continuously suppressed NK cells throughout dosing. Additionally, the overall response rate (ORR) appeared higher for the 16-mg/kg dose compared with the 8-mg/kg dose, based on early preliminary data from Part 2 of Study GEN501 and from Study MMY2002 (both ongoing) as of a cutoff date of 24 January 2014. In Study GEN501, the ORRs (ie, partial response [PR] or greater) were 11% and 40% for the 8-mg/kg (n=28) and 16-mg/kg (n=15) dose regimens, respectively. For the Study MMY2002, the unconfirmed ORRs for the 8-mg/kg and 16-mg/kg dose regimens were similar to those observed in GEN501. In addition, VGPRs were observed for 7 of 30 subjects treated with the 16-mg/kg dose in those 2 studies. VGPR had not been observed at lower dose levels. These preliminary data support that full target saturation at the 16-mg/kg dose is needed to achieve higher and deeper response rates. In addition, the 16-mg/kg dose and schedule was shown to have an acceptable and manageable safety profile for the approximately 30 subjects for whom preliminary data were available in Studies GEN501 and MMY2002, and no additive toxicity has been observed in the Phase 1 dose escalation when comparing the safety from 16 mg/kg dose cohort with lower dose cohorts.

4. STUDY POPULATION

4.1. General Considerations

Between 42 and 58 subjects will be enrolled in this study, depending on the number of dose levels included during dose escalation in Phase 1. It is estimated that the screen failure rate will be 25% and that between 56 and 78 subjects will be screened in order to enroll the expected number.

4.2. Inclusion Criteria

Before entering Phase 1 of the study, subjects must:

- 1. Have relapsed multiple myeloma after receiving a minimum of 2 and a maximum of 4 prior lines of therapy and be eligible for treatment with Len/Dex.
- 2. Have measurable levels of M-component, defined as serum M-component $\geq 1.0 \text{ g/dL}$ and/or urine M-component $\geq 200 \text{ mg/24-hour sample}$.
- 3. Be \geq 18 years of age.
- 4. Have an Eastern Cooperative Oncology Group (ECOG) performance status of 0, 1, or 2 (Attachment 1).
- 5. Have a life expectancy of ≥ 3 months.
- 6. Provide signed informed consent after receipt of oral and written information about the study and before any study-related activity is performed.

Before entering Phase 2 of the study, subjects must:

- 1. Have received at least 1 prior line of therapy for multiple myeloma (refer to Attachment 2).
 - Have achieved a response (PR or better) to at least one prior regimen.
 - Have documented evidence of progressive disease (PD) as defined by the IMWG criteria on or after their last regimen.
- 2. Have measurable levels of M-component, defined as serum M-component $\geq 1.0 \text{ g/dL}$ and/or urine M-component $\geq 200 \text{ mg/24-hour sample}$.
- 3. Be \geq 18 years of age.
- 4. Have an ECOG performance status score of 0, 1, or 2 (Attachment 1).
- 5. Have a life expectancy of ≥ 3 months.
- 6. Provide signed informed consent after receipt of oral and written information about the study and before any study-related activity is performed.

4.3. Exclusion Criteria

Before entering the study, subjects must not:

- 1. Have previously received an allogenic stem cell transplant.
- 2. Have received auto-SCT within 12 weeks before the first infusion.
- 3. Have received antimyeloma treatment, radiotherapy, or any experimental drug or therapy within 2 weeks before the first infusion.
- 4. Have discontinued lenalidomide due to any treatment-related adverse event or be refractory to any dose of lenalidomide.

Refractory to lenalidomide is defined as either:

- Subjects whose disease progresses within 60 days of lenalidomide, or
- Subjects whose disease is nonresponsive while on any dose of lenalidomide. Nonresponsive disease is defined as either failure to achieve at least an MR or development of PD while on lenalidomide.
- 5. Have experienced prior DVT of ≥ Grade 3 according to the National Cancer Institute's Common Terminology Criteria for Adverse Events, version 4.0 (CTCAE).
- 6. Have experienced prior PE.
- 7. Have had past or current malignancy, except for:
 - cervical carcinoma of Stage 1B or less;
 - noninvasive basal cell or squamous cell skin carcinoma;
 - malignant melanoma with a CR of > 10 years duration;
 - prostate cancer with a current prostate-specific antigen level < 0.1 ng/mL;
 - any curable cancer with a CR of > 5 years duration.
- 8. Have any current serious infectious disease requiring systemic treatment.
- 9. Have clinically significant cardiac disease, including:
 - unstable angina;
 - acute myocardial infarction within 6 months of the Screening Visit (before the first infusion);
 - congestive heart failure (Class III or IV as classified by the New York Heart Association; Attachment 3);
 - a known decreased cardiac ejection fraction of < 50%;

- a screening 12-lead electrocardiogram (ECG) reading showing a baseline QT interval as corrected by Fridericia's formula (QTcF) > 470 msec for females or > 450 msec for males or a complete left bundle branch block (defined as a QRS interval ≥ 120 msec in left bundle branch block form).
- 10. Have a significant, concurrent, uncontrolled medical condition including, but not limited to, renal (except as related to multiple myeloma), hepatic, hematologic (except as related to multiple myeloma), gastrointestinal, endocrine, pulmonary, neurologic, cerebral, or psychiatric disease.
- 11. Be exhibiting clinical signs of meningeal involvement of multiple myeloma.
- 12. Have known severe chronic obstructive pulmonary disease or asthma (defined as a forced expiratory volume in 1 second [FEV1] <60% of predicted normal) or persistent asthma.
- 13. Have a history of significant cerebrovascular disease.
- 14. Have known to be seropositive for human immunodeficiency virus (HIV) or have active hepatitis B or hepatitis C.
- 15. Have screening laboratory test results as the following:
 - absolute neutrophil count ≤1.5 × 10^9 /L;
 - hemoglobin level $\leq 80 \text{ g/L} (\leq 5 \text{ mmol/L});$
 - platelet count $< 75 \times 10^9/L$
 - alanine aminotransferase (ALT) \geq 2.5 times the upper limit of normal (ULN);
 - alkaline phosphatase level $\geq 2.5 \times ULN$;
 - direct bilirubin level $\geq 2 \times ULN$;
 - creatinine clearance (CrCl) ≤ 60 mL/min within 7 days before the Screening Visit (before the first infusion);
 - potassium level < 3.0 mEq/L.
- 16. Have received granulocyte-colony stimulating factor (G-CSF) or granulocyte/macrophage-colony stimulating factor support for < 1 week or pegylated G-CSF for < 2 weeks before the Screening Visit or before the first infusion.
- 17. Have received a cumulative dose of corticosteroid \geq 200 mg (dexamethasone, or equivalent doses of prednisone) within 2 weeks before the first infusion.

- 18. Have a known hypersensitivity to components of the study drug or combination therapy, or have known allergies, hypersensitivity, or intolerance to monoclonal antibodies or human proteins, or their excipients (refer to Investigator Brochure 2013), or have known sensitivity to mammalian-derived products.
- 19. Have plasma cell leukemia or Waldenström's macroglobulinemia.
- 20. Have previously received daratumumab, or other anti-CD38 therapies.
- 21. Be known to have any contraindications to receiving lenalidomide (as specified in the lenalidomide label).
- 22. Have received treatment with any nonmarketed drug substance within 4 weeks before the first infusion.
- 23. Be currently participating in any other interventional clinical study.
- 24. Be known or suspected of not being able to comply with the study protocol (eg, because of alcoholism, drug dependency, or psychological disorder).
- 25. Be breastfeeding female.
- 26. Have a positive pregnancy test at the Screening Visit or before the first infusion.
- 27. Be unwilling to use adequate contraception for 4 weeks before the first infusion of daratumumab, during the study, and for 6 months after the last infusion of daratumumab if a female of childbearing potential. Adequate contraception is defined as hormonal birth control or an intrauterine device. For subjects in the US, the use of a double-barrier method during interruption periods and for at least 4 weeks after the end of treatment is also considered adequate. Subjects in the EU must follow the Pregnancy Prevention Programme.
- 28. Be males unwilling to use a latex condom during any sexual contact with females of childbearing potential during and for 6 months after the last infusion of daratumumab, even after having undergone a successful vasectomy.

NOTE: Investigators should ensure that all study enrollment criteria have been met at screening. If a subject's status changes (including laboratory results or receipt of additional medical records) after screening but before the first dose of study drug is given such that he or she no longer meets all eligibility criteria, then the subject should be excluded from participation in the study. Section 17.4, Source Documentation, describes the required documentation to support meeting the enrollment criteria.

5. TREATMENT ALLOCATION AND BLINDING

5.1. Subject Allocation Procedures

In Phase 1, subjects will be allocated to the dose escalation cohorts in a standard 3 + 3 study design. In Phase 2, subjects will be enrolled to an expansion cohort. Allocation of subjects in both Phases 1 and 2 will be controlled by the contract research organization (CRO).

When a potential subject is identified at a site, the site personnel must contact the CRO regarding the subject. If there is an opening in the currently enrolling cohort, the site will be given approval to start the screening process.

If there is no opening in the currently enrolling cohort, the CRO will place the subject on a list of potential subjects. If another subject fails the screening process, the CRO will alert the site that has the next subject on the waiting list. If the subject is still eligible, the site will be given approval to start the screening process.

5.2. Blinding

As this is an open study, blinding procedures are not applicable.

6. DOSAGE AND ADMINISTRATION

The start of a cycle is defined as the start of any of the study treatments (ie, daratumumab or Len/Dex). If all treatments are held, then it should be reported as a cycle delay.

6.1. Daratumumab

Daratumumab will be administered as an IV infusion. Each subject's dose will be calculated based on the subject's weight rounded to the nearest kilogram, ie, assigned cohort dose in $mg/kg \times body$ weight in kg. The dose does not need to be recalculated for weight changes that are <10% from baseline. The weight will be used to determine the number of vials required for dosing. The pharmacist will then calculate the required volume of daratumumab from the number of vials needed for each subject. For subjects whose body mass index is greater than 30 kg/m^2 , the investigator should use a weight that, based on the subject's height, corresponds to a maximum body mass index of 30.

For Phase 1, daratumumab will be given as follows:

- Cycle 1: Day 0 (predose infusion), Day 1 (first full-dose infusion), and Days 8, 15, and 22 of a 28-day cycle
- Cycle 2: Days 1, 8, 15, and 22 of a 28-day cycle
- Cycles 3-6: Days 1 and 15 of a 28-day cycle for 4 cycles or until the subject experiences unacceptable toxicity or disease progression, whichever comes first
- Cycles 7+: Day 1 of a 28-day cycle until the subject experiences unacceptable toxicity or disease progression, whichever comes first

For Phase 2, daratumumab will be given as follows:

- Cycle 1: Day 1 (first full-dose infusion), and Days 8, 15, and 22 of a 28-day cycle
- Cycle 2: Days 1, 8, 15, and 22 of a 28-day cycle
- Cycles 3-6: Days 1 and 15 of a 28-day cycle for 4 cycles or until the subject experiences unacceptable toxicity or disease progression, whichever comes first
- Cycles 7+: Day 1 of a 28-day cycle until the subject experiences unacceptable toxicity or disease progression, whichever comes first Table 5 and Table 6 provide recommendations for the rate of infusion.

Table 5: Phase 1 Infusion Rate Recommendations

Predose	Infusions	First Full-do	ose Infusion ^a	Subsequent Full-dose Infusions ^a			
Time (minutes)	Rate (mL/hour)	Time	Rate (mL/hour)	Time (minutes)	Rate (mL/hour)		
		(minutes)					
0 - 240	12.5	0 - 60	50	0 - 60	50°		
		61 – 180	100	61 - 120	100		
		181 -	150 ^b	121 - 180	150		
				181 -	200		
Total volume	50 mL	Total volume	1000 mL	Total volume	1000 mL		

^a Additional details for administration times and rates for the full-dose infusions will be provided in the administration guidelines.

Table 6: Phase 2 Infusion Rate Recommendations

	e Infusion for y 20 Subjects ^a		e Infusion for y 10 Subjects ^a	Subsequent Full-dose Infusion for all subjects ^a			
Time (minutes)	Rate (mL/hour)	Time	Rate (mL/hour)	Time (minutes)	Rate (mL/hour)		
		(minutes)					
0 - 60	50	0 - 60	50°	0 - 60	50°		
61 - 180	100	61 – 120	100	61 - 120	100		
181 -	150 ^b	121 – 180	150	121 - 180	150		
		181 -	200	181 -	200		
Total volume	1000 mL	Total volume	500 mL	Total volume	500 mL		

^a Additional details for administration times and rates for the full-dose infusions will be provided in the administration guidelines.

The sponsor or IDMC may modify the predose infusion, infusion rates, or premedications, prospectively based upon the information collected to date from this and other studies. Additional details for administration times and rates, as well as premedications, will be provided in the administration guidelines.

If the infusion is uneventful after 2 hours at a rate of 150 mL/hour, the investigator may increase the infusion rate to 200 mL/hour.

If no infusion reactions occurred during the last full-dose infusion, the infusion rate may start at 100 mL/hour at the investigator's discretion.

If the infusion is uneventful after 2 hours at a rate of 150 mL/hour, the investigator may increase the infusion rate to 200 mL/hour.

^c If no infusion reactions occurred during the last full-dose infusion, the infusion rate may start at 100 mL/hour at the investigator's discretion.

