9.2.1.4. Electrocardiogram	Text deleted: Digital ECGs will be transmitted from the sites electronically to a central laboratory (eResearch Technology, Inc) for a treatment-blinded measurement of the cardiac rhythm and assessment of morphology by a central cardiologist.			
Rationale: Alignment with other daratumumab protocols.				
12.6.1. All Adverse Events	Text revised to state that adverse events will be collected within 30 days of the last dose of any component of the treatment regimen.			
Rationale: Subjects may continue daratumumab treatment beyond 24 cycles.				
Table 2 (Phase 2 Time and Event Schedule)	Changed range of Study visits column header from "7-24" to "7+".			
Rationale: Minor errors were noted				
Throughout the protocol	Minor grammatical, formatting, or spelling changes were made.			

Amendment 5 (26 February 2014)

This amendment is considered to be substantial based on the criteria set forth in Article 10(a) of Directive 2001/20/EC of the European Parliament and the Council of the European Union.

The overall reason for the amendment: This amendment included defining the change in sponsor to Janssen Research & Development (JRD) and converting to the JRD protocol template. Additionally 10 of the approximately 30 subjects enrolled on Phase 2 will have shortened infusion times for the first daratumumab infusion to evaluate the safety and incidence of infusion related reactions when infusion time is shortened. Eligibility criteria have also been modified to remove the cap placed on prior lines of therapy to allow a broader population to be studied in Phase 2.

Applicable Section(s) Description of Change(s)											
Rationale: JRD has taken over resp daratumumab.	onsibility of this study from Genmab A/S in a partnership effort to develop										
Global	Changed sponsor name from Genmab A/S to Janssen Research & Development										
	edules were revised to reflect the changes made in the assessments for the study y by adding separate tables for assessment in Phase 1 and Phase 2.										
Table 1 and Table 2 Time and Event Schedules	Revised Table 1 (Time and Event Schedule) to reflect changes in the protocol. Added Table 2 (Time and Event Schedule for Phase 2 which includes pharmacokinetic/immunogenicity and exploratory biomarker assessments) for clarity										
Rationale: A secondary objective w	ras added to evaluate immunogenicity using JRD analysis methods.										

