By using a PK model based on the available data, in which the "sink" is represented by a nonlinear route of clearance and assuming that the "sink" remains unchanged during therapy, predictions were made for alternative dosing schedules. For weekly infusions at a dose level of 8 mg/kg, it is expected that the effect of the "sink" will become relatively small, the C_{max} of daratumumab will be in the range of 200 to 300 μ g/mL, trough concentrations will be around 100 μ g/mL, and no major accumulation will occur. Furthermore, at the proposed dose schedule (where the dose interval after Week 8 is extended to 2 weeks), no accumulation of daratumumab is expected, even if the "sink" diminishes during therapy.

The starting dose of the daratumumab component in this combinational study will be 2 mg/kg. This dose corresponds to ¼ of the dose currently being investigated (8 mg/kg) and ½ of the

highest dose that has been approved by the external IDMC (4 mg/kg) in the ongoing GEN501 monotherapy study.

To prevent cytokine release syndrome, a predose infusion will be administered the day before the first full-dose infusion of daratumumab. The predose infusion will be 10% of the full dose, but never more than 10 mg in total. In Phase 2, the predose will not be administered. Further measures to prevent cytokine release syndrome will include premedication with antihistamines, acetaminophen, and dexamethasone before each infusion (both predose and full dose).

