6.6. Management of Infusion-related Reactions

Subjects who experienced AEs during the infusion must be treated according to the investigator's judgment and best clinical practice. The infusion may be paused or the infusion rate may be decreased, which may cause a longer-than-anticipated infusion time. Overnight stays at the hospital because of slow infusions times should not be reported as an SAE.

The study staff at the site should be prepared to intervene in case of the occurrence of any infusion reaction, and resuscitation equipment must be available at bedside. Special attention should be paid during each subject's first full-dose infusion.

For patients at higher risk of respiratory complications (eg, patients with COPD who have an FEV1 <80%, or subjects with mild asthma), the following post infusion medications should be considered:

- Antihistamine (clemastine 1 mg IV, cetirizine 10 mg PO, or equivalent) on the first and second days after all full-dose infusions
- Salbutamol aerosol
- Controller medications (eg, inhaled corticosteroids ± long-acting beta agonists for patients with asthma; long-acting bronchodilators such as tiotropium or salmeterol ± inhaled corticosteroids for patients with chronic obstructive pulmonary disease)

In addition, these at-risk patients may be hospitalized for monitoring for up to 2 nights after an infusion. If patients are hospitalized, their FEV1 should be measured before discharge. If these

patients are not hospitalized, follow-up telephone calls should be made to monitor their condition twice daily on the first and second days after all full-dose infusions.

6.6.1. Infusion-related Reactions of Grade 1 or 2

If the investigator judges the AE to be related to the infusion, the infusion should be paused. When the subject is stable, the infusion may be restarted at the investigator's discretion. Upon restart, the infusion rate should be half of that employed before the interruption.

Subsequently, the infusion rate may be increased at the investigator's discretion as described in Table 5 and Table 6.

If the subject experiences a Grade 2 or higher event of bronchospasm or laryngeal edema, the subject must be withdrawn from treatment.

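### Table 6 attaches a condition about a previous full-dose infusion to the first infusion of about 10 Phase 2 subjects, so their shortened schedule is not fully defined

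*Protocol*

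**What the plan says.** Protocol Section 6.1, Table 6, has three columns for Phase 2: a first infusion for about 20 subjects, a first infusion for about 10 subjects, and "Subsequent Full-dose Infusion for all subjects". The first two headers are clipped in the text available to us. The summary of Amendment 5 confirms what the middle column is: "10 of the approximately 30 subjects enrolled on Phase 2 will have shortened infusion times for the first daratumumab infusion". It gives the purpose as evaluating safety and infusion reactions when the infusion is shortened.

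In the middle column and in the subsequent-infusion column, the rate for the first 60 minutes is 50 mL/hour with a footnote marker. In the 20-subject column it is a plain 50. Footnote c reads: "If no infusion reactions occurred during the last full-dose infusion, the infusion rate may start at 100 mL/hour at the investigator's discretion".

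Three other statements fix what has happened to a Phase 2 subject before this infusion:

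- Section 6.1, Phase 2 schedule: "Cycle 1: Day 1 (first full-dose infusion), and Days 8, 15, and 22 of a 28-day cycle".
- Section 3.2.3.1: "In Phase 2, the predose will not be administered".
- Section 4.3, criterion 20, excludes subjects who "Have previously received daratumumab, or other anti-CD38 therapies".

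**The concern.** A rule that depends on how the last full-dose infusion went cannot be applied to a subject who has never had one. A site using the 10-subject column has two options. It can ignore the footnote as inapplicable, or it can reason that no reaction has occurred and that the faster start is open at the investigator's discretion. The protocol text does not choose between them.

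This matters more here than it would elsewhere in the dosing section. The study's primary objective is safety, and these 10 subjects were separated out so that a shorter first infusion could be judged on its infusion reactions. If the starting rate may be either of two values, reactions seen in the group cannot be attributed to one known schedule.

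**Working it through.** **1. Is the marker footnote c?** In the text available to us it appears as a degree sign after 50. Three things support reading it as c. The same sign stands on the starting rate for subsequent infusions in Table 5. Footnotes a and b are already used, a on the column headers and b on the 150 mL/hour step. Only c concerns a starting rate.

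**2. Where does it appear?**

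| Table and column | First-hour rate | Marker on it | Earlier full dose? |
|---|---|---|---|
| Table 5, first full dose (Phase 1) | 50 mL/hour | none | no |
| Table 5, subsequent | 50 mL/hour | yes | yes |
| Table 6, first, about 20 subjects | 50 mL/hour | none | no |
| Table 6, first, about 10 subjects | 50 mL/hour | yes | no |
| Table 6, subsequent | 50 mL/hour | yes | yes |

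In four of the five columns, the marker appears exactly when an earlier full dose exists. The 10-subject column is the exception. Its rates and total volume match the subsequent-infusion column line for line.

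**3. Does the condition have a referent?** Cycle 1 Day 1 is the first full dose, no predose is given in Phase 2, and earlier daratumumab is excluded. So it has none.

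**4. What schedules follow?** The duration is the time needed for the rate steps to deliver the total volume.

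- 10-subject column as tabulated, 500 mL: 50 + 100 + 150 = 300 mL by 3 h; the remaining 200 mL at 200 mL/hour takes 1 h. Total 4.0 h.
- Footnote applied, later steps keep their clock times: 100 + 100 + 150 = 350 mL by 3 h; 150/200 = 0.75 h. Total 3.75 h.
- Footnote applied, each later step moves one hour earlier: 100 + 150 = 250 mL by 2 h; 250/200 = 1.25 h. Total 3.25 h.
- 20-subject column, 1000 mL: 50 + 2 × 100 = 250 mL by 3 h; 750/150 = 5 h. Total 8.0 h. With the footnote b step-up after 2 h at 150 mL/hour: 250 + 300 = 550 mL by 5 h; 450/200 = 2.25 h. Total 7.25 h.

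Share of the bag given in the first hour: 50/500 = 10% as tabulated, 100/500 = 20% with the footnote, and 50/1000 = 5% in the 20-subject column.

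**5. Would the planned analysis show which schedule was used?** SAP Section 6.1.2.1 presents infusion reactions for each phase by system organ class, preferred term and grade, and by type of pre-infusion steroid. It does not split them by first-infusion schedule or starting rate. SAP Section 4.4 summarizes infusion duration, but Section 2.6.8 counts interruptions in that duration, so a difference of 0.25 h (4.0 − 3.75) would not reliably identify the starting rate.

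**The case against.** The case on the other side is substantial, and much of it stands.

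- **The marker is probably a copying slip.** A condition on the last full-dose infusion presupposes one. Where there is none, the plain reading is that the option is not triggered and the tabulated rate applies. A reader might infer that the protocol authorizes a doubled starting rate at first exposure because the condition is met by default. The text does not go that far; it only fails to rule it out.
- **Section 6.6.** A reader might see a conflict with "Special attention should be paid during each subject's first full-dose infusion". There is none: that section asks for vigilance and sets no rate.
- **Other documents.** Both tables are recommendations, footnote a defers details of times and rates to administration guidelines that are not among the documents, and the sponsor or IDMC may change rates prospectively. The guidelines may already settle the point.
- **Timing.** By Amendment 8 every subject has had at least 24 months of study drug or has stopped, so no Phase 2 first infusion is still to come. A correction changes no future infusion.
- **No planned estimate depends on it.** The SAP defines no reaction rate for the 10 subjects and no comparison with the other 20. Pauses and rate changes were allowed in any case, so delivered schedules would have varied.

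These arguments limit the consequences. They do not supply the missing referent, and they do not help someone reading the results to know which first-hour rate the 10-subject group received.

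**Conclusion.** The point holds as a limited defect in a stated dosing rule: footnote c, as attached to the 10-subject first-infusion column, has a condition that cannot be applied. It affects about 10 of about 30 Phase 2 subjects. The two readings differ by a factor of two in the first-hour rate (50 or 100 mL/hour) and by 0.25 h or 0.75 h in the planned 4.0 h, depending on how the later steps move. The value of correcting it now lies in the record and in interpreting these subjects' reactions.

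This rests on reading the marker as c, which is well supported but comes from imperfect text, and on the administration guidelines not having resolved the matter.

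Two further inferences are not supported. The documents give no basis for saying how many of the 10, if any, started at 100 mL/hour. Nor do they show that the starting rate was recorded: Protocol Section 7 lists start and stop times, the amount infused, and reasons for interruption or rate decrease, but not the rate at the start.

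**What to change.** Reconcile the Table 6 marker, footnote c and the administration guidelines, so that no first-infusion column carries a condition about a previous infusion. The clinical team decides which starting rate is right. If the table is not reissued, a note in the study report stating which reading was in force would serve.

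In the report, present infusion reactions at the first infusion by assigned schedule (about 10 against about 20 subjects), as a description only. Add a breakdown by actual starting rate where it was captured. If it was not, check source records or state that the first-hour rate in this group is unknown.

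The cost is one table correction or explanatory note and one extra tabulation. A source-record check on about 10 infusions is needed only if the rate is not in the database.
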